7.2. Procedures for Participant Discontinuation

In rare instances, it may be necessary for a participant to permanently discontinue the study intervention. If the study intervention is permanently discontinued, the participant should, if at all possible, remain in the study to be evaluated for safety, tolerability, and efficacy outcomes. See the Schedule of Assessments (SoA) for data to be collected at the time of discontinuation of study intervention and follow-up, and for any further evaluations that need to be completed. Participants who discontinue the study intervention should undergo the following procedures:

1. **Documentation of Reason for Discontinuation:** The reason for discontinuation must be documented in detail, including any adverse events, lack of efficacy, non-compliance, or personal reasons.
2. **Outcome data:** Every effort will be made to collect outcome data on all participants who withdraw from treatment for whatever reason. If participants withdraw from treatment, all endpoint assessments will be carried out at the point of drop-out and at the 12-month endpoint unless consent is withdrawn.

As PATH-1 is unblinded there will be no procedures related unblinding of the participants

8. Required Actions and Follow-Up

1. Reporting:

- All events of ALT or AST $\geq 3 \times$ ULN and total bilirubin $\geq 2 \times$ ULN (with $> 35\%$ direct bilirubin) or ALT or AST $\geq 3 \times$ ULN and INR > 1.5 or GFR < 30 mL/min/1.73 m²) and acute kidney injury (e.g., serum creatinine increase by 1.5 times baseline or oliguria) must be reported to the sponsor in an expedited manner.
- Additionally, QTc prolongation ≥ 460 milliseconds for males or ≥ 470 milliseconds for females, significant arrhythmias (e.g., Torsade de Pointes), or bradycardia with heart rate < 50 bpm and associated symptoms (e.g., syncope) must also be reported within 24 hours. Confirmed gastrointestinal bleeding, such as melena, hematemesis, or peptic ulcers, persistent severe symptoms not resolving with management (e.g., uncontrolled vomiting), should be reported as serious adverse events (SAEs) when applicable. All adverse events must be documented in the case report form (CRF) and reported to the study sponsor regulatory authorities according to local requirements.

2. Follow-Up

- Repeat laboratory or clinical assessments (e.g., liver enzymes, eGFR, ECGs, or GI evaluations) will be conducted weekly or bi-weekly, depending on the severity of the abnormality, until resolution or stabilization.
- Comprehensive clinical evaluations, including symptom assessments, will be performed as needed.

3. Continuation of the study intervention

- Continuation of the study intervention of the study intervention will be considered only if the abnormality resolves or improves to a clinically acceptable level, as determined by the investigator and sponsor.

4. Participant communication: Participants will be informed of the findings, any changes to their treatment plan, and the rationale for either resuming or discontinuing the study intervention.

8.1.1. Temporary Discontinuation

Abnormalities identified during regular monitoring, including but not limited to liver chemistry changes, renal function decline, cardiac abnormalities (e.g., QTc prolongation), or gastrointestinal symptoms, will be assessed by the investigator to determine the appropriate course of action. This may include enhanced monitoring, additional diagnostic evaluations, or discontinuation of the study intervention.

8.1.2. Study Intervention Restart or Rechallenge After Stopping Criteria Are Met

Study intervention restart or rechallenge in participants who have met stopping criteria for liver chemistry, ECG abnormalities, renal dysfunction, or other safety-related are not allowed.

8.2. Lost to Follow up

A participant will be considered lost to follow-up if the participant repeatedly fails to return for scheduled visits and is unable to be contacted by the study site.

The following actions must be taken if a participant fails to return to the clinic for a required study visit:

- The site must attempt to contact the participant and reschedule the missed visit as soon as possible, counsel the participant on the importance of maintaining the assigned visit schedule and ascertain whether the participant wishes to and/or should continue in the study.
- Before a participant is deemed lost to follow-up, the investigator or designee must make every effort to regain contact with the participant (where possible, with telephone calls, and if necessary, a certified letter to the participant's last known mailing address or local equivalent methods). These contact attempts should be documented in the participant's medical record.
- Should the participant continue to be unreachable, the participant will be considered to have withdrawn from the study.
- Site personnel may look up vital status in The Norwegian Cause of Death Registry or the medical journal.

If vital status is determined as deceased, this will be documented, and the participant will not be considered lost to follow-up.

9. Study Assessments and Procedures

Consented patients will undergo a screening visit within 28 days of the planned baseline visit. For women of childbearing potential, a negative serum pregnancy test will be required within 1 day prior to receiving the first dose of study drug. Only those patients who complete screening and meet study eligibility criteria at baseline will be randomized 6:2 to receive phenserine or donepezil in an open-label manner. The first dose of study medication will be taken in the clinic, and the participants will be instructed on how to continue dosing at home until their next visit.

Participants will visit the clinic for safety and other planned study assessments at 2-week intervals through the 8-week treatment period, as detailed in the Schedule of Activities (Table 1).

Patients who withdraw or discontinue from the study before Week 8 will have an early termination visit within one week of discontinuation that includes safety follow-up. For participants who complete the study, a final follow-up safety assessment will be conducted within one week after completion of dosing.

- Study procedures and their timing are summarized in the SoA. Protocol waivers or exemptions are not allowed.
- Adherence to the study design requirements, including those specified in the SoA, is essential and required for study conduct.
- All screening evaluations must be completed and reviewed to confirm that potential participants meet all eligibility criteria. The investigator will maintain a screening log to record details of all participants screened and to confirm eligibility or record reasons for screening failure, as applicable.
- Procedures conducted as part of the participant's routine clinical management (eg, blood count) and obtained before signing of the ICF may be utilized for screening or baseline purposes provided the procedures met the protocol-specified criteria and were performed within the timeframe defined in the SoA.
- In the event of a significant study-continuity issue (eg, caused by a pandemic), alternate strategies for participant visits, assessments, medication distribution and monitoring may be implemented by the sponsor or the investigator, as per local health authority/ethics requirements.

The maximum amount of blood collected from each participant over the duration of the study, including any extra assessments that may be required, will not exceed 642 mL.

Repeat or unscheduled samples may be taken for safety reasons or for technical issues with the samples.

9.1. Screening Visit

During the screening visit, participants will undergo a series of assessments to determine their eligibility for the study.

- During this visit, and before any study procedures are performed, informed consent will be obtained from the participant and caregiver to ensure they understand the study's objectives and willingly agree to participate.
 - This includes a medical evaluation with a detailed medical history review including: concomitant medications, physical examination, Vital signs
 - Safety laboratory tests
 - Urinalysis
 - Physical Exam
 - Neurological Exam, including mental status
 - ECG
 - MRI (if not performed within 2 years)
 - Modified C-SSRS
 - Lumbar puncture (Optional, if not performed previously) for CSF analysis of Alzheimer pathology and storage for subsequent biomarker assessment
 - Venepuncture for blood analysis
- Participants will also be evaluated for their cognitive status using MMSE and CDR
- Review of inclusion/exclusion criteria including confirmation of pathology with validated biomarkers
- If participants are taking any anti-dementia medications, they will be instructed on the washout period required before baseline assessments. If considered relevant, re-screen can be performed.

9.2. Randomization

- Participants will be randomized before, or during, the baseline visit.
- Participants will be randomized and allocated study treatment via Viedoc in a 6:2 ratio

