4.1. Overall Design

Consented patients will undergo a screening visit within 28 days of the planned baseline visit. (For women of childbearing potential, a negative serum pregnancy test will be required within 1 day prior to receiving the first dose of study drug). Only those patients who complete screening and meet study eligibility criteria at baseline will be randomized 6:2 to receive phenserine or donepezil in an open-label manner. The first dose of study medication will be taken in the clinic, and the participant will be instructed on how to continue dosing at home until their next visit.

Participants will visit the clinic for safety and other planned study assessments at 2-week intervals through the 8-week treatment period, as detailed in the Schedule of Activities ([Table 1](#)).

Patients who withdraw or discontinue from the study before Week 8 will have an early termination visit within one week of discontinuation that includes safety follow-up. For participants who complete the study, a final follow-up safety assessment will be conducted within one week after completion of dosing.

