6.3. Assignment to Study Intervention

In this study, participants will be randomized 6:2 to phenserine or donepezil in an open-label manner. Drug Dispensing and Dosing Instructions

Randomized subjects will be dispensed a single bottle of phenserine or donepezil drug product on Day 0 following all baseline assessments and confirmation of eligibility. Each participant will take the first dose in clinic and be instructed on how to continue dosing at home through the next two weeks (5 mg bd for the phenserine group and 5 mg od for the donepezil group). As shown in Figure 1, at the end-of-Week 2 visit, participants will undergo safety and tolerability assessments, and will be tested to determine their cholinesterase inhibition level. Based on tolerability, participants in the phenserine treatment group may be titrated to the next higher dose level (10 mg bd) for the next two weeks of treatment, while participants in the donepezil arm will continue the 5 mg od regimen. Adequate supplies will continue to be provided to the participants at this visit and in future visits to ensure they have adequate study drug (with an appropriate overage) to ensure that there are no disruptions in their daily dosing regimen through to the next study visit. At the end-of-Week 4 visit, and based on safety/tolerability assessments, participants in the phenserine arm may be escalated to 10 mg tds through to the end-of-Week 8 visit and participants in the donepezil arm may escalate to 10 mg od and remain at that dose through the remainder of the study (i.e., end of Week 8, as long as it is tolerated. Participants in both arms will return for follow-up assessments at the end-of-Week 6.. At the end-of-Week 8 visit, all participants will undergo final on-drug study assessments and will then return to the site for a final safety follow-up visit within 1 week of the last study-drug dose.

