6.3.1. Allocation- procedure to randomize a participant

Both the subjects and the site staff will know which treatment they are assigned. Participants and site staff, will be blinded to the results of the exosomal and blood/CSF biomarker evaluations until the study is completed.

Participants will be identified by a unique study ID. Personal identifiable data (such as name, address, and other contact details) will be collected, but will be stored separately from the research data and will be destroyed as per applicable regulations when the project is concluded. Data will be managed by the University Hospital Stavanger clinical trials unit, following all relevant data protection guidelines and all relevant Clinical Trial Regulations. Data will be collected and stored electronically in accordance with the Data Protection Act 2018 and ICH GCP E6 R2. Data will be cleaned and validated appropriately, with a full Data Protection Impact Assessment (DPIA) undertaken along with development of a comprehensive Data management Plan (DMP) before the first participant is recruited.

[figure not shown]
The computer-generated randomized allocation sequence will be produced by an independent, unblinded statistician and imported into the Viedoc Electronic Data Management System (EDCS). The unblinded statistician will generate randomisation lists using using R v4.2 as implemented in <https://icostatistics.shinyapps.io/randlist/> Participants will be screened for eligibility and first included by study physicians after informed consent. After study inclusion the participant will be randomized via Viedoc. The participant will be allocated treatment arm via Viedoc and receive the assigned IMP treatment at the first baseline visit by a study nurse. The study nurse will record the date of IMP distribution and the time and date of the first dose administered in Viedoc.

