6.4. Blinding

The study intervention will be open label. No blinding will be performed. Participants and site staff will, however, will be blinded to the results of the exosome and blood/CSF biomarker evaluations until the study is completed.

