9.3. Baseline Visit

At the baseline visit, participants will undergo a comprehensive set of initial assessments. These include:

- Standard medical assessment: with the same evaluations as in the screening visit (except neurological examination).
- Participants will be evaluated for their cognitive status using MOCA
- Pregnancy test if applicable
- Adverse events evaluation
- Venepuncture for blood analysis
- Administration of cognitive tests FLAME Memory Composite
- The study drug will be dispensed to the participant

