2.4 Timing of Outcome Assessments

The timing of all outcome assessments is predefined in the study protocol and summarized in the Schedule of Activities (SoA) (Protocol Section 1.3, Table 1). Outcome measures are collected at screening, baseline, and at scheduled on-treatment and follow-up visits during the 8-week treatment period and safety follow-up.

For all clinically planned outcome measures, visits should occur within the predefined visit windows. Assessments performed outside the allowable visit window will be considered protocol deviations, unless otherwise justified and documented. Only assessments obtained within the protocol-specified windows will be used for primary and secondary analyses.

The target days and visit windows relevant for efficacy, pharmacodynamic, pharmacokinetic, and safety analyses are defined as follows:

Visit Label	Visit Window
Screening	Within 28 days prior to baseline
V1: Baseline / Randomization	Day 0
V2: Week 2	Day 14 ± 3 days
V3: Week 4	Day 28 ± 3 days
V4: Week 6	Day 42 ± 3 days
V5: Week 8 / End of Treatment	Day 56 ± 3 days
Safety Follow-up / EOS	Within 28 days after last dose

Assessments collected outside the visit window will not be included in the primary analysis but may be listed and summarized descriptively.

3 Study Design Overview

- Design: Open-label, randomized (6:2), parallel-group Phase 1b study
- Treatment Arms:
 - Phenserine (dose-escalation up to 10 mg TDS)
 - Donepezil (5–10 mg OD)
- Treatment Duration: 8 weeks
- Sample Size: n = 16 (Phen: n=12; Donepezil: n=4)

Given the exploratory nature and small sample size, all analyses will be descriptive, and estimation focused.

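### Protocol Section 9.2 allows randomisation before the baseline visit, contradicting Sections 4.1 and 9, Table 1 and SAP 2.4, and nothing places open-label allocation after baseline cognitive testing

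*Protocol*

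**What the plan says.** Section 9.2 of the protocol sets the timing of allocation: "Participants will be randomized before, or during, the baseline visit". Section 4.1 gives a different rule, repeated at the start of Section 9: "Only those patients who complete screening and meet study eligibility criteria at baseline will be randomized 6:2". Table 1 marks the inclusion/exclusion check at screening and again at baseline, and marks randomisation at baseline. SAP 2.4 labels the Day 0 visit "V1: Baseline / Randomization".

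Section 6.3 does give an order, but for a later step: the drug is dispensed "on Day 0 following all baseline assessments and confirmation of eligibility". Section 6.3.1 has the Viedoc randomisation follow inclusion, with the drug handed over at the baseline visit. It does not say where the baseline tests fall.

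Allocation is open once made. Section 6.3.1 says: "Both the subjects and the site staff will know which treatment they are assigned". Section 6.4 says: "The study intervention will be open label. No blinding will be performed". The baseline visit in Section 9.3 includes the two cognitive measures: "Participants will be evaluated for their cognitive status using MOCA" and "Administration of cognitive tests FLAME Memory Composite". Table 1 schedules both at baseline and Week 8 only.

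**The concern.** In an open-label trial, the main protection for a baseline measurement is that it is taken before anyone knows the arm. Section 9.2 lets a site give that up and still comply with the protocol. Two things are then exposed.

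- **Baseline cognition.** MoCA and FLAME each have one pre-treatment value, and the SAP analyses change from it. If the participant or the MoCA rater knows the arm, effort or scoring can shift, and the shift enters every change score with the opposite sign.
- **Final inclusion.** The eligibility re-check at baseline involves judgement. If the arm is already known, that judgement can depend on it. A participant who is allocated but never dosed falls outside the mITT population (Protocol 10.3.1, SAP 4.3), so analysing by allocated arm does not bring that person back.

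Appendix 8 shows how the arm becomes known in practice. Once a participant is randomised to donepezil, the study nurse asks that participant for a letter of authorisation to collect the prescription.

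**Working it through.** **1. The plan's own figure.** Protocol 10.3 assumes a difference of 2.45 SD, 80% power and alpha 0.05 (two-sided per Section 10.3.1), and states 4 per arm. The normal approximation gives 2 × (1.960 + 0.842)² / 2.45² = 2 × 7.85 / 6.00 = 2.6, so 3 per arm. Exact two-sample t power is 0.62 at 3 versus 3 and 0.82 at 4 versus 4, so 4 per arm is reproduced. At the planned 12 versus 4 it is 0.976. None of these depends on when allocation is released, so the point is about bias and not about power.

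**2. The passages side by side.**

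| Place | Position of randomisation | After baseline eligibility check? | After MoCA, FLAME and baseline samples? |
|---|---|---|---|
| Protocol 9.2 | Before or during the baseline visit | Not required | Not required |
| Protocol 4.1 and 9 | Once eligibility is met at baseline | Yes | Not stated |
| Table 1 | Baseline column | Same visit, no order | Same visit, no order |
| SAP 2.4 | Day 0 | Not stated | Not stated |
| Protocol 6.3 | Orders dispensing only | Dispensing: yes | Dispensing: yes |
| Protocol 6.3.1 | After inclusion, in Viedoc | Screening and inclusion come first; baseline re-check not mentioned | Not stated |

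Two separate results follow. A site cannot randomise before the visit and also wait for eligibility to be met at that visit, so Section 9.2 contradicts Sections 4.1 and 9, Table 1 and SAP 2.4. In addition, no row puts randomisation after the cognitive tests or the baseline samples. That gap remains even if the contradiction is settled in favour of Day 0.

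**3. Size of the exposure.** The documents give no figure for an expectation effect, so the shifts below are assumptions. If one participant's baseline score moves by k SD, the mean of an arm of n moves by k/n.

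| Assumed shift k | Donepezil, n = 4 | Phenserine, n = 12 |
|---|---|---|
| 0.5 SD | 0.125 SD | 0.042 SD |
| 1 SD | 0.25 SD | 0.083 SD |
| 2 SD | 0.5 SD | 0.167 SD |

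The same arithmetic applies to inclusion: one decision influenced by known allocation concerns 1/4 = 25% of the donepezil arm and 1/12 = 8.3% of the phenserine arm. These figures show how sensitive the small arm is. They do not estimate a bias.

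**The case against.** The strongest reply is that the rest of the protocol already prevents most of this. Sections 4.1 and 9 tie randomisation to eligibility at baseline, Table 1 and the SAP put it on Day 0, and Section 9 requires adherence to the schedule and allows no waivers. Eligibility, including biomarker confirmation, is reviewed at screening (Section 9.1), so only the baseline re-check is exposed. This stands as a limit. A reader might infer that the protocol simply permits randomising people whose eligibility is unconfirmed. It does not: one section permits it and others forbid it. Those other sections do not cancel Section 9.2 either, and none of them deals with the order of the cognitive tests.

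The second reply is that little of consequence is affected. Section 3 and SAP 4.5 make cognition exploratory, and the SAP interprets it descriptively. Section 9.12 says staff do no more than set up FLAME. Week 8 testing is done with the arm known in any case. The primary endpoint is a laboratory measure, with participants and site staff blinded to its results until the study is completed. All of this stands, and it keeps the point modest. It does not protect the MoCA rating or the participant's own effort.

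Two stronger readings are tempting, and the documents do not support them.

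- A reader might infer a loss of precision: losing one donepezil participant would raise the standard error of the arm difference from √(1/12 + 1/4) = 0.577 SD to √(1/12 + 1/3) = 0.645 SD, or 12%. Section 10.1 replaces participants who leave before taking drug, with the aim of holding the target sample size, so this loss is not what the plan implies. The figure also measures precision and not bias.
- A reader might infer that correct ordering would stop people refusing their arm. It would not. In an open-label trial a participant can still decline after allocation and before the first dose, leave the mITT population and be replaced.

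**Conclusion.** The point holds as an internal contradiction plus a missing order. Section 9.2 cannot be reconciled with Sections 4.1 and 9, Table 1 and SAP 2.4. No passage requires allocation to follow the baseline MoCA, FLAME or exosome and AChE samples. A site following Section 9.2 can therefore reveal the arm before the only pre-treatment MoCA and FLAME values and before the baseline eligibility re-check.

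The consequence is possible bias in the exploratory change-from-baseline cognition, and possible influence of known allocation on who is finally included. Expectation should have little effect on the primary exosome measurement itself. The size of any bias is unknown, and the shifts in the arm means rest on assumed changes in a single score. Sample size, power and alpha are unchanged. The protocol should be corrected on this point, but it does not undermine the primary analysis.

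**What to change.** Remove from Section 9.2 the words that allow randomisation before the visit. That alone is not enough, because randomising during the visit still allows allocation ahead of testing. Add one sentence stating that Viedoc releases the allocation on Day 0 only after the final eligibility check, the baseline MoCA and FLAME, and the baseline exosome and AChE samples are recorded as complete, and before the drug is dispensed. Bring Sections 4.1, 6.3, 6.3.1 and 9, Table 1 and SAP 2.4 into line with it.

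The cost is one protocol sentence, the matching edits and a form-order check in Viedoc. The practical downside is that drug preparation moves into the Day 0 visit. For donepezil, the authorisation letter and pharmacy collection described in Appendix 8 would have to be completed between allocation and the in-clinic first dose.
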